7.2 Statistical Analyses

Data analysis from this multi-center clinical trial will be performed to characterize 2D and 4D CEUS as a follow-up imaging tool for the evaluation of residual tumoral blood flow in patients with HCC treated with TACE.

Our statistical analysis will address three major questions:

1. Does 2D and 4D CEUS 1-2 weeks post TACE yield sensitivity and specificity greater than 90% for identifying residual tumor blood flow, thereby providing reliable earlier identification (relative to the current clinical standard) of patients in need of retreatment?
2. Does 2D and 4D CEUS 1 month post TACE yield sensitivity and specificity greater than 90% for identifying residual tumor blood flow, thereby providing an accurate, safe, and cost-effective imaging alternative for identifying TACE patients in need of retreatment?
3. Are quantifiable biomarkers generated by parametric imaging of 2D and 4D CEUS exams able to differentiate between fully treated and incompletely treated masses by measuring blood flow kinetics?

The first three cases at each institution will be used as reader training cases and will not be included in the final analysis. In the event of all cases showing identical response (i.e. all incompletely or completely treated), the first case with an alternative outcome will be substituted for the 9th case. Following reader training, each reader (all of whom have previous experience with CEUS and volumetric ultrasound) will be asked to evaluate all 201 remaining cases. 2D and 4D CEUS exams will be read separately and only after randomization. 2D cases will be viewed in a standard DICOM viewer, while 4D cases will be viewed in GE's 4D View software. Readers will first be asked to review both the patient's baseline CE-MRI/CT and CEUS exams to identify the size and location of the treated mass. Following baseline review, each reader will review the 1-2 week and 1 month CEUS exam (in random order). Intratumoral blood flow will be assessed as present or not present. Readers will then be asked to interpret the patient's 1 month follow-up CE-MRI/CT images and again evaluate the need to retreat based on residual blood flow. Finally, when available, readers will review subsequent CE-MRI/CT imaging studies (up to six months post TACE). MRI/CT evaluations will be based on mRECIST criteria. All imaging studies will be read twice by each

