reader. Studies will be presented in random order. The second round reads will be performed at least one month after the first. Outcomes will be defined as incompletely treated (i.e. requiring retreatment) based on (in order of preference of reference standard): a) pathological examination of explanted livers demonstrating live tumors; b) tumor enhancement seen with CT or MR and confirmed via angiography during retreatment; c) tumor growth on 6 month follow-up CE-CT/MRI; or d) asymmetrical or nodular tumor enhancement on CE-MRI/CT on 6 month follow-up. Incomplete treatment on CEUS (2D or 4D) will be evaluated by each reader and evidenced by the tumor showing either residual blood flow after treatment or nodular peripheral blood flow.

For questions 1-2, sensitivity (the ability to detect patients in need of retreatment) and specificity (the ability to identify patients who do not require retreatment) will first be calculated on a reader by reader basis. Four 2 x 2 tables will be constructed comparing the need for re-treatment based on the clinical gold standard described above and CEUS, tabulating true positives, false positives, false negatives, and true negatives. A table will be created for CEUS at 1-2 weeks and 1 month for both 2D and 4D CEUS and used to calculate sensitivity, specificity, accuracy, positive predictive value, and negative predictive value. Statistical significance between the reference standard and each of the 4 CEUS groups will be determined using a McNemar test. These values will also be calculated based on the majority decision (i.e. 4 or more readers in agreement). In the event of discordant readings during this analysis, tumor outcome will be decided by consensus by the two readers at TJU. Differences between techniques (2D vs. 4D) and time points (1-2 weeks vs. 1 month post treatment) will be determined by comparing areas under the receiver operating characteristic curves for each modality/time point based on necessity of tumor retreatment. Intra-rater and inter-rater variability will be calculated using a Shrout and Fleiss Interclass Correlation [Shrout and Fleiss 1979]. Finally, a logistical regression and analysis of variance will be performed to determine if significant variations exist between individual sites (to determine operator dependence), lesion size (tumor size dependency) or between patients treated with cTACE vs. DEB-TACE (treatment dependency).

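### Split CEUS majority reads are settled by two readers who, in the planned order, have already read that patient's follow-up MRI/CT, and nothing restricts that step to the CEUS images

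*Combined protocol and SAP*

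**What the plan says.** Section 7.2 (Statistical Analyses) sets the reading sequence; the Synopsis and section 6.5 repeat it. Each reader "will be asked to evaluate all 201 remaining cases". After the baseline review, "each reader will review the 1-2 week and 1 month CEUS exam (in random order"). The next step is follow-up cross-sectional imaging: "Readers will then be asked to interpret the patient's 1 month follow-up CE-MRI/CT images and again evaluate the need to retreat" on residual blood flow. Lastly, "when available, readers will review subsequent CE-MRI/CT imaging studies (up to six months post TACE").

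Sensitivity and specificity are calculated first for each reader separately. Section 7.2 then adds: "These values will also be calculated based on the majority decision (i.e. 4 or more readers in agreement"). For discordant readings in that analysis, the tie-break is that "tumor outcome will be decided by consensus by the two readers at TJU".

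The reference standard has four levels in order of preference: (a) explant pathology, (b) CT or MR enhancement confirmed by angiography at retreatment, (c) growth on 6-month CE-CT/MRI, and (d) asymmetrical or nodular enhancement on 6-month CE-MRI/CT.

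Section 5.4, the only section on blinding, deals with the trial drug. The random order and the minimum one-month gap in section 7.2 apply to the two rounds of reads. Neither is stated for the consensus step.

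**The concern.** An accuracy estimate is credible only if the index test is called without knowledge of the reference. The plan protects the individual first-round CEUS reads by placing them ahead of the follow-up MRI/CT. It does not give the tie-break the same protection. A split is known only when all readers have finished a case, and by then the stated order has taken both TJU readers through imaging that contributes to the reference. They have also voted in the split that they are asked to settle.

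The cases affected are those where CEUS is hardest to call. If recall or review of the MRI/CT influences the consensus, the expected direction is agreement with the reference, which raises both sensitivity and specificity. Questions 1 and 2 ask whether both exceed 90%. The majority decision is the only reader-pooled result the plan defines, and the plan does not say whether that result or the individual readers' results answer the question.

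**Working it through.** **1. Does the sequence follow from the text?** All readers read all cases, so the two TJU readers do. Per case the order is CEUS, then 1-month CE-MRI/CT, then later CE-MRI/CT when available. A discordance among readers can be identified only after all of them have read the CEUS exams. No text holds back the TJU readers' MRI/CT reads, limits what they view at consensus, or uses other adjudicators. Reference levels (b), (c) and (d) rest at least in part on CT/MRI. Followed as written, the plan lets readers who have seen reference-related imaging settle the split calls.

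**2. Reproduce the plan's power.** Inputs from section 7.2.1: null 0.90, alternative 0.98, alpha 0.05, and the table row for 200 patients with 133 diseased, leaving 200 − 133 = 67 non-diseased. The rule is the smallest r with P(X ≥ r | n, 0.90) ≤ 0.05, one-sided.

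- Sensitivity, n = 133: r = 126 (at most 7 errors), actual alpha 0.0385, power 0.9945.
- Specificity, n = 67: r = 65 (at most 2 errors), actual alpha 0.0307, power 0.8494.

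Both match the plan's table, so its 99% and 85% are reproduced. One-sided 0.025 would give 0.982 and 0.612, which do not match.

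**3. Illustrate the effect on specificity.** Let s be the share of negatives that are ties, b the specificity in the rest, and q the probability that the consensus gives the correct call. Then specificity = (1 − s)·b + s·q, and the chance of passing is P(at most 2 errors in 67). The values of s and q are assumptions. So is applying 97% or 98% to the untied cases; the plan gives 98% only as its overall alternative.

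| s | b | Specificity, q = 0.75 | Pass | Specificity, q = 0.90 | Pass | Gain (points) |
|---|---|---|---|---|---|---|
| 2% | 97% | 0.9656 | 0.59 | 0.9686 | 0.65 | 5 |
| 2% | 98% | 0.9754 | 0.77 | 0.9784 | 0.82 | 5 |
| 5% | 97% | 0.9590 | 0.48 | 0.9665 | 0.61 | 13 |
| 5% | 98% | 0.9685 | 0.65 | 0.9760 | 0.78 | 14 |

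For example, in the third row, 0.95 × 0.97 + 0.05 × 0.75 = 0.9590. In patients, 5% of 67 is 3.35 and 2% is 1.34. Gains are taken from unrounded probabilities.

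The extreme contrast at s = 5% and b = 97% is q = 0.50 (specificity 0.9465, pass 0.30) against q = 1.00 (specificity 0.9715, pass 0.70).

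**4. Error-control view.** Suppose majority-read accuracy is exactly 90% when ties are settled at 50% correct. With informed resolution it becomes 0.90 + s·(q − 0.5). The chance of wrongly declaring it above 90% is then:

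| s | q | Sensitivity (≥126/133) | Specificity (≥65/67) |
|---|---|---|---|
| any | 0.50 | 0.039 | 0.031 |
| 5% | 0.75 | 0.096 | 0.060 |
| 2% | 1.00 | 0.081 | 0.053 |
| 5% | 1.00 | 0.212 | 0.113 |

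**5. How common might ties be?** The number of readers is not stated. As an assumption, six independent readers split 3–3 in 20·p³(1 − p)³ of cases: 1.5% at per-reader accuracy p = 0.90 and 8.2% at p = 0.80. The assumed 2% to 5% lies within that range.

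**The case against.** The tie-break sentence does not say which images the TJU readers view or that MRI/CT is open to them. Its reference to the analysis can be read as naming the majority-decision analysis, with no statement about timing. Prior exposure is inferred from the per-case order, and any influence could depend on recalling one case among 201, with studies shown in random order. This stands as far as it goes: bias is a possibility left open, and neither its direction nor its size is shown. It does not remove the exposure, which follows from the reading order, or the absence of a safeguard.

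A reader might infer that the trial's accuracy results as a whole are biased. The documents do not support that. The reader-by-reader estimates come first and do not use the tie-break; only the additional majority-decision analysis does. Nor is the limit of 2 errors in 67 a stated decision rule for that analysis. It is back-calculated from the sample-size section, while the test named for the 2 × 2 tables is McNemar's.

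A reader might also take 0.30 versus 0.70 as the likely effect. It pairs a coin toss by experienced CEUS readers with perfect knowledge of the reference. Neither end is realistic: level (a) is explant pathology, level (b) needs angiographic confirmation, and the later imaging is read only when available.

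Finally, the rule settles the tumor outcome, and section 7.2 also uses the word outcome for the reference standard. In context the CEUS majority call is the more natural reading, but the text does not settle it. If the reference were meant, CEUS readers would be setting it, which is a different dependence problem to which the arithmetic above would not apply.

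**Conclusion.** The point holds as an unprotected step in a secondary presentation of the primary accuracy question. As written, the plan allows the most ambiguous CEUS calls to be settled by readers who have seen imaging that feeds reference levels (b) to (d), and this can inflate majority-read sensitivity and specificity. The size cannot be derived from the documents. Under the stated assumptions, the illustrative gain in the chance of passing on specificity is about 5 to 14 percentage points; the 0.30 versus 0.70 contrast is an outer bound at one setting. These figures also assume that the rule settles the CEUS call and that the majority read is tested by the exact binomial rule used for the sample size. The undefined trigger matters too: if any disagreement goes to consensus, more cases are exposed than if only cases without four agreeing readers do. The correction is worth making before reading starts. If ties prove rare, reporting their number would largely settle the matter.

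**What to change.** Amend section 7.2, with matching text in the Synopsis:

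- State that the tie-break settles the CEUS call and does not set the reference outcome.
- Define a discordant reading as one where no four readers agree, and state the number of readers.
- Hold the TJU consensus on CEUS images alone, after all readers' first-round CEUS reads of the case and before the TJU readers open that case's 1-month or later CE-MRI/CT. If that order is impractical, replace the consensus with a fixed numeric tie rule.
- Report the number of ties for each modality and time point, and add a sensitivity analysis counting every tie as an error. That analysis is a worst-case bound and should be labelled as one.

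No new patients, readers or images are needed. The main cost is scheduling: the TJU readers' MRI/CT reads must wait until every reader has completed the first-round CEUS reads of the case, which changes the per-case sequence. Majority-read accuracy may also come out somewhat less favourable.

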examination will be obtained from the patient's referring physician. If the subject is a woman of childbearing potential, she will have a urine pregnancy test prior to each CEUS study (the results of which will be made available to the subject prior to study initiation). In the event a patient presents with a lesion that is expected to be difficult to view on ultrasound (for example, smaller lesions located high on the liver dome), grayscale ultrasound imaging will quickly be performed to ensure the lesion is visible on ultrasound and that the patient is suitable for study inclusion.

Patients will undergo a total of three separate CEUS exams. These exams will consist of the baseline study prior to TACE therapy, a study 1-2 weeks post treatment that will coincide with clinical post-procedure follow-up by the interventional radiologist, and a study approximately one month post treatment when patients return for clinically scheduled CE-CT/MRI follow-up. If the patient fails to show up for the 1-2 week CEUS exam, they will not be excluded from the final ultrasound exam. Procedures and equipment for this trial will be used in accordance with standard clinical protocols and good clinical practices already in place at our hospitals.

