For statistical question 3, all quantitative parameters will be compared between fully treated and incompletely treated masses using a Student's t-test. Additionally, lesions that demonstrate lack of residual enhancement at 1 month, but show recurrence at 6 month follow-up, will be compared to completely treated masses to determine if quantitative CEUS parameters can detect this lower level of residual disease. Statistical analysis will be performed with assistance from the biostatistician co-investigator using Stata 12.0 (Stata Corp, College Station, TX) with p values < 0.05 considered statistically significant after a Bonferroni-type adjustment for multiple tests. These statistical tests will answer our three major questions regarding the sensitivity and specificity of 2D and 4D CEUS as an imaging tool for the follow-up of TACE

at 1-2 weeks and 1 month (specific aims 1-2), as well as the influence of operator, reader, tumor size, and embolization material.

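### 2D versus 4D and early versus 1-month CEUS are compared only by ROC area, with no ROC input named and no paired estimate of the sensitivity and specificity differences

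*Combined protocol and SAP*

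**What the plan says.** Section 2 states the primary objective as the sensitivity and specificity of 2D and 4D CEUS at 1-2 weeks and at 1 month. Questions 1 and 2 in Section 7.2 put this as a threshold; the first asks "Does 2D and 4D CEUS 1-2 weeks post TACE yield sensitivity and specificity greater than 90% for identifying residual tumor blood flow".

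For comparisons between techniques and between time points, Section 7.2 has one sentence, repeated in the Synopsis (Statistical Methodology). Such differences "will be determined by comparing areas under the receiver operating characteristic curves for each modality/time point based on necessity of tumor retreatment". No score, reader or pooling rule is named as the input to the curve.

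The CEUS read is binary: "Intratumoral blood flow will be assessed as present or not present". Incomplete treatment on CEUS is likewise a yes/no judgement, "evaluated by each reader and evidenced by the tumor showing either residual blood flow after treatment or nodular peripheral blood flow". No confidence scale is described.

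The other planned analyses do not cover these contrasts:
- "Statistical significance between the reference standard and each of the 4 CEUS groups will be determined using a McNemar test". That sets each condition against the reference, not one CEUS condition against another.
- The logistic regression and analysis of variance concern site, lesion size and type of TACE.
- The quantitative parameters are assigned to t-tests.
- The majority decision (four or more readers) is written for the 2 x 2 table values and is not stated to feed the ROC curve.

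Results are "considered statistically significant after a Bonferroni-type adjustment for multiple tests", without a list of the tests in the family.

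**The concern.** The objective is written in terms of sensitivity and specificity, while the only head-to-head method works on a summary that adds the two together. A missed residual tumor and a false call for retreatment are different errors, and a comparison of techniques or of timing should show how each one changes.

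With a binary read, the area test could report no difference between 2D and 4D, or between an early and a 1-month exam, while the tables show different sensitivities and specificities. The reader would then have no planned estimate or interval to judge whether those differences exceed chance. Because the ROC input is not stated, the comparison also cannot be run as written without a choice that the plan leaves open.

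**Working it through.** **Inputs.** Section 7.2.1 gives 201 analysed patients, prevalence 66.7%, null sensitivity (Se) and specificity (Sp) of 90%, and alternatives of 98%. It prints both 135 and 133 patients needing retreatment. Since 0.667 x 201 = 134, I use 134 reference-positive and 67 reference-negative patients.

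**The plan's own power figure.** A one-sided exact binomial test at 0.05 reproduces the N = 200 row:
- n = 133: reject at 126 or more correct; actual alpha 0.0385, power 0.9945 (stated as 99%).
- n = 67: reject at 65 or more correct; actual alpha 0.0307, power 0.8494 (stated as 85%).

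These are one-sample powers against 90%. No power is given for any head-to-head contrast.

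**Area on one binary read.** The curve has one interior point, so area = (Se + Sp)/2.
- 98/90 (Se/Sp): (0.98 + 0.90)/2 = 0.94. 90/98: (0.90 + 0.98)/2 = 0.94. Difference 0.
- 98/94 against 90/98: 0.96 - 0.94 = 0.02, from an 8-point fall in Se and a 4-point rise in Sp.

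**Rejection rates by simulation.** The plan names no test for correlated areas. I assumed z = (dSe + dSp)/sqrt(Var dSe + Var dSp), with dSe and dSp the paired differences and paired variances, two-sided. For Se and Sp separately I used exact McNemar tests between the two conditions. All patients have both exams and errors are independent unless stated. The Se/Sp pairs are assumptions, because the plan gives no expected difference.

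At an unadjusted 0.05, for 98/90 against 90/98, the area test rejects in 5-6% of trials. Paired McNemar on Se rejects in 75% (independent errors) to 96% (maximally correlated errors), and on Sp in 35% to 44%.

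The family behind the Bonferroni-type adjustment is not listed, so the next table assumes one. The area test alone over four contrasts uses 0.05/4. Area plus paired Se and Sp tests over four contrasts uses 0.05/12 each and counts any rejection.

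| Se/Sp compared | Areas | Area alone, 0.05/4 | Any of three, 0.05/12 |
|---|---|---|---|
| 98/90 vs 90/98 | 0.94, 0.94 | 1.5% | 41% |
| 98/94 vs 90/98 | 0.96, 0.94 | 7% | 37% |
| 98/98 vs 90/98 | 0.98, 0.94 | 38% | 43% |
| 98/98 vs 98/90 | 0.98, 0.94 | 23% | 14% |
| 98/98 vs 90/90 | 0.98, 0.90 | 81% | 72% |
| 98/98 vs 94/94 | 0.98, 0.94 | 29% | 19% |
| 98/94 vs 94/98 | 0.96, 0.96 | about alpha | 6% |

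With error correlation 0.3 the pattern is the same. The two columns become about 2% and 62% in the first row, 10% and 59% in the second, and 95% and 90% for 98/98 against 90/90.

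**Precision of a paired difference.** For 98% against 90% with independent errors, the discordant proportion is 0.98 x 0.10 + 0.02 x 0.90 = 0.116 and the squared difference is 0.08² = 0.0064. The 95% half-width is 1.96 x sqrt((0.116 - 0.0064)/n):
- n = 134 (Se): 5.6 points.
- n = 67 (Sp): 7.9 points.

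**What the planned McNemar test sees.** It responds to an imbalance of false negatives and false positives within one condition. At 90/98 the expected counts are 134 x 0.10 = 13.4 and 67 x 0.02 = 1.3, and it rejects in 90% of trials at 0.05. At 98/90 they are 134 x 0.02 = 2.7 and 67 x 0.10 = 6.7, and it rejects in 15%. This is indirect evidence of a trade-off, not a test of the difference between conditions.

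**The case against.** The strongest case for the plan is that ROC area is a defensible single summary. It is the better test when both measures move the same way (81% against 72% above) or only specificity falls (23% against 14%). The contrasts are not among the three major questions, and the trial is sized on one-sample tests. Se and Sp are tabulated for all four conditions, by reader and by majority, so a trade-off would not be hidden. All of this stands, and it is why the area test should stay.

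The ROC input might also be something other than one binary read. A count of positive readers, or a 0/1/2 score from each reader's two reads, would give a curve with several points, to which the (Se + Sp)/2 identity does not apply. None of these is specified. With an assumed six or seven readers behaving symmetrically, mirrored shifts still gave equal areas (0.978 each for six readers at an intraclass correlation of 0.6), but that symmetry is built into the model, so it settles nothing about real readers.

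Three stronger readings are tempting and not supported:
- A reader might infer that the area test cannot detect opposing changes at all. Cancellation is complete only for equal and opposite changes on a single binary read.
- A reader might infer that a trade-off is likely here. The documents predict none; Section 7.2.1 assumes 98% for both measures.
- A reader might infer that confirmatory paired tests would repair the problem. In the assumed 12-test family they reject in only 41% and 37% of trials for the two 8-point opposing cases and about 6% for a 4-point mirrored change, and they cost power elsewhere.

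**Conclusion.** The point holds in a limited form. ROC area is the only stated method for comparing 2D with 4D and the two time points, its input is not named, and no paired estimate, interval or test of the Se or Sp difference is planned. If the input is a single binary read, the test has no power beyond alpha against equal and opposite changes, and reduced power against partly opposing ones. The area identity is exact. The rejection rates rest on assumed Se/Sp pairs, 134 and 67 patients with both exams, an assumed form of area test and an assumed Bonferroni family.

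The one-sample analyses for questions 1 and 2 are unaffected. What is missing is an answer to secondary contrasts on the scale in which the objective is written, so this is a modest improvement and not a flaw in the primary analysis.

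**What to change.** Keep the ROC-area comparison as the formal test at its planned alpha, and state its input: one reader's binary read, the majority read, a count of positive readers, or a repeat-read score.

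For each of the four contrasts (2D against 4D at each time point; 1-2 weeks against 1 month within each technique), add:
- the paired difference in sensitivity among reference-positive patients and in specificity among reference-negative patients, on the majority read, each with a 95% confidence interval;
- restriction to patients with both exams, with that number reported, because the Synopsis says "If the patient fails to show up for the 1-2 week CEUS exam, they will not be excluded from the final ultrasound exam";
- one lesion per patient, or an interval clustered by patient, because the Synopsis (Trial Procedures) allows up to two lesions to be imaged.

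Label any exact McNemar p-values for these differences as supportive and outside the Bonferroni family. State that a non-significant area comparison alone will not be reported as no difference.

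The cost is SAP wording and slightly more analysis, with no new exams, reads or readers. The intervals will be wide, especially for specificity. Making the paired tests confirmatory would be a different choice: in the assumed 12-test family it would bring the power losses tabulated above.

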7.2.1 Sample Size Justification

As the most clinically important aims, aims 1-2 will be used as the basis for the sample size analysis, where each patient represents an independent data point used to evaluate the technique's sensitivity and specificity at both 1-2 weeks and 1 month follow-up times. Based on our pilot studies using 2D CEUS to evaluate TACE performed using Lipiodol [Kono et al. 2007] or drug-eluting-beads [Shaw et al. 2014], we expect to encounter a patient population in which up to 67% of patients require retreatment. A sample size analysis was performed using a binomial test with One-Sample Sensitivity and Specificity Analysis in NCSS/PASS 2008 (NCSS, East Kaysville, UT) to estimate the number of cases required to produce a over 85% power for this study. This analysis assumes sensitivity and specificities of 98%, an alpha of 0.05, prevalence of disease of 66.7%, and null sensitivity and specificities of 90%. Results from this analysis are provided in tabular format below.

Preva- ---- Power ----		Sample	--- Sensitivity ---		--- Specificity ---		----- Alpha -----			P
Size	H0 Sens. Spec.	H1 N1 and N	H0 Se0	H1 Se1	Sp0	Sens. Sp1	Spec. Target	lence Actual	Actual	P
0.0000	0.0000	7								
10	0.9000	0.9800	0.9000	0.9800	0.0500	0.0000	0.0000	0.6670		
0.0000	0.0000	13								
20	0.9000	0.9800	0.9000	0.9800	0.0500	0.0000	0.0000	0.6670		
0.0000	0.0000	20								
30	0.9000	0.9800	0.9000	0.9800	0.0500	0.0000	0.0000	0.6670		
0.0000	0.0000	27								
40	0.9000	0.9800	0.9000	0.9800	0.0500	0.0000	0.0000	0.6670		
0.5134	0.0000	33								
50	0.9000	0.9800	0.9000	0.9800	0.0500	0.0309	0.0000	0.6670		
0.4457	0.0000	40								
60	0.9000	0.9800	0.9000	0.9800	0.0500	0.0148	0.0000	0.6670		
0.7581	0.0000	47								
70	0.9000	0.9800	0.9000	0.9800	0.0500	0.0440	0.0000	0.6670		
0.7135	0.0000	53								
80	0.9000	0.9800	0.9000	0.9800	0.0500	0.0259	0.0000	0.6670		
0.6619	0.5455	60								
90	0.9000	0.9800	0.9000	0.9800	0.0500	0.0138	0.0424	0.6670		
0.8494	0.5134	67								
100	0.9000	0.9800	0.9000	0.9800	0.0500	0.0307	0.0309	0.6670		
0.8202	0.4735	73								
110	0.9000	0.9800	0.9000	0.9800	0.0500	0.0190	0.0203	0.6670		
0.9231	0.4457	80								
120	0.9000	0.9800	0.9000	0.9800	0.0500	0.0353	0.0148	0.6670		
0.9027	0.4195	87								
130	0.9000	0.9800	0.9000	0.9800	0.0500	0.0211	0.0108	0.6670		
0.9608	0.7581	93								
140	0.9000	0.9800	0.9000	0.9800	0.0500	0.0382	0.0440	0.6670		

0.9492	0.7358	100							
150	0.9000	0.9800	0.9000	0.9800	0.0500	0.0237	0.0338	0.6670	

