0.9791	0.7135	107							
160	0.9000	0.9800	0.9000	0.9800	0.0500	0.0374	0.0259	0.6670	
0.9735	0.6839	113							
170	0.9000	0.9800	0.9000	0.9800	0.0500	0.0255	0.0181	0.6670	
0.9893	0.6619	120							
180	0.9000	0.9800	0.9000	0.9800	0.0500	0.0382	0.0138	0.6670	
0.9857	0.8879	127							
190	0.9000	0.9800	0.9000	0.9800	0.0500	0.0250	0.0421	0.6670	
0.9945	0.8494	133							
200	0.9000	0.9800	0.9000	0.9800	0.0500	0.0385	0.0307	0.6670	

A total of 201 patients will be used in the final analysis for this study (the first 9 will be used as training cases and excluded), of which 135 (66.7%) will require retreatment. A total sample size of 201 (which includes 133 subjects with the disease) achieves 99% power to reject the null hypothesis for sensitivity, and 85% power to reject the null hypothesis for specificity.

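### At the assumed 98% accuracy each CEUS group has about four errors, too few for the planned logistic regression and ANOVA to settle site, lesion-size and TACE-type dependence

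*Combined protocol and SAP*

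**What the plan says.** Section 7.2 (repeated in the Synopsis under Statistical Methodology) states that "a logistical regression and analysis of variance will be performed to determine if significant variations exist between individual sites". Site is read as operator dependence, lesion size as tumor-size dependence, and cTACE versus DEB-TACE as treatment dependence. The section does not name the dependent variable, the reading used (one reader, the majority, or all reads), the coding of lesion size, whether the factors enter together or singly, or any method for sparse data or repeated reads. It closes by saying that the tests will answer the main questions "as well as the influence of operator, reader, tumor size, and embolization material". The Introduction also describes the multi-center sample as sufficient to investigate operator and reader dependencies.

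Section 7.2.1 sizes the trial on aims 1–2 only, "where each patient represents an independent data point". "This analysis assumes sensitivity and specificities of 98%, an alpha of 0.05, prevalence of disease of 66.7%, and null sensitivity and specificities of 90"%. "A total of 201 patients will be used in the final analysis for this study", "of which 135 (66.7%) will require retreatment" (the next sentence gives 133), and this "achieves 99% power to reject the null hypothesis for sensitivity, and 85% power to reject the null hypothesis for specificity". No power is given for the dependency analyses.

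**The concern.** A regression of CEUS correctness on patient and site factors draws its information from the errors. If CEUS performs as assumed, there are very few. Two site terms, one TACE-type term and one size term make four slopes, supported by about four errors per CEUS group. Whenever a site or a TACE type has no errors, ordinary logistic regression has no finite estimate for it. Where the model does fit, it has little power against moderate differences.

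The trial could therefore finish with a non-significant or non-converging result and no basis for saying whether accuracy depends on operator, lesion size or embolic material, although the plan lists those answers among its outputs. Operator independence matters in practice for a technique proposed as an alternative to MRI/CT.

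**Working it through.** **Inputs.** Sensitivity and specificity 98%, null 90%, alpha 0.05, prevalence 66.7%, 201 analysed patients (section 7.2.1); three sites, at most 100 patients each (section 4). The split by site and by TACE type is not fixed, so ranges are shown.

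**1. The plan's own figure.** Take the smallest count r with P(X ≥ r | 0.90) ≤ 0.05, one-sided exact binomial.
- n = 133: r = 126, actual alpha 0.0385, power 0.9945.
- n = 67: r = 65, actual alpha 0.0307, power 0.8494.

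These reproduce the stated 99% and 85%.

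**2. Errors the success rule allows.** 133 − 126 = 7 false negatives and 67 − 65 = 2 false positives. The limits are the same with 134 or 135 positives and with 66 or 68 negatives. A CEUS group meeting both targets therefore has at most 9 errors. Two false positives cannot cover three sites, so in any group meeting the specificity target at least one site has none, and a three-site specificity model with one result per patient cannot have finite estimates.

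**3. Expected errors at 98%.** 201 × 0.02 = 4.02 (5th–95th percentile 1 to 8; P(10 or more) = 0.8%). False negatives: 134 × 0.02 = 2.68. False positives: 67 × 0.02 = 1.34, with P(none) = 0.98^67 = 25.8%. Per slope: 4.02/4 ≈ 1.

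**4. Does the joint model have a finite fit?** Simulated trials were checked for separation by linear programming, using one correct/incorrect result per patient, two site terms, TACE type and continuous size. Percentage with no finite fit:
- All 201 patients, sites 67/67/67: about 62% with TACE type 50:50, 66% at 70:30, 83% at 90:10.
- Sites 97/52/52: 67–84%. Sites 97/97/7: 92–95%.
- Reference-positive patients only (134): 80–85%. Reference-negative only (67): 95–97%.

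The main cause is a site with no errors: 1 − (1 − 0.258)^3 = 59% for the even split.

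**5. One factor at a time.** Site alone fails in that same 59%. TACE type alone at 100/101 fails in 0.98^100 + 0.98^101 − 0.98^201 = 0.133 + 0.130 − 0.017 ≈ 25%. Size alone usually fits (no errors at all: 0.98^201 = 1.7%).

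**6. Other accuracies, and pooled reads.**
- At 95% accuracy (10 errors), non-fit is about 8–10% with even sites and TACE type 50:50. It rises to 44% across the first two site splits and TACE-type splits up to 90:10, and is 71–80% for 97/97/7.
- At 90% (20 errors) the corresponding ranges are 0.3–15% and 47–54%.
- At 98% with six pooled reads per patient (number assumed) and within-patient correlation 0.3, 0.5 or 0.7, overall non-fit is about 4%, 9–12% and 25%. Across those correlations it is 15–53% for sensitivity alone and about 60–88% for specificity alone.

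**7. Power for a site difference, even split, alpha 0.05.**

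| Two sites at 98%, third at | Overall accuracy | Sensitivity | Specificity |
|---|---|---|---|
| 94% | 22% (ANOVA), 30% (likelihood ratio) | 21% | 9% |
| 90% | 59% (ANOVA), 63% (likelihood ratio) | 49% | 25% |

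Sensitivity and specificity columns use the likelihood-ratio test. For TACE type at 98% versus 94%, a Fisher test has 17% power. The plan's Bonferroni-type adjustment does not state the number of tests. At an illustrative 0.05/4 = 0.0125, the 94% cases drop to 8% (site ANOVA) and 6% (TACE type).

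**The case against.** The strongest reply is that the plan fixes neither a joint model nor a unit of analysis. Taken factor by factor, size and a balanced TACE type can usually be fitted. Every study is read twice by each reader, so a read-level model is open to the investigators and would usually fit for overall correctness. The 98% is a design assumption, and at 95% non-fit is uncommon with even splits. All of this stands, and it rules out saying that the analyses generally cannot be fitted. It does not rescue the plan as written: no clustering is specified, so ordinary regression on pooled reads would overstate precision, and specificity models stay sparse even with pooling.

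A reader might also infer three stronger things.
- **That the ANOVA and every site test fail.** They do not. ANOVA on 0/1 results can be computed whenever there is any error, and a likelihood-ratio test for site needs no finite coefficients. The weakness is low power and a poor fit to the ANOVA assumptions.
- **That a different retreatment mix would create false site differences in overall correctness.** Under the plan's equal 98% values, correctness is 98% at any mix. The point has force only if sensitivity and specificity differ.
- **That a null result will be reported as no dependence.** No section says so. What the plan does say is that the tests will answer the question, and it gives no guard against that reading.

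These analyses come last, and the trial is not sized on them. Low power there does not touch the primary sensitivity and specificity questions.

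**Conclusion.** The concern holds in a limited form. At the plan's assumed accuracy there are about four errors per CEUS group, and at most nine in a group that meets both targets. With one result per patient, the joint ordinary logistic model lacks a finite fit in about 62% of trials overall and in most trials for sensitivity or specificity separately. Power against a site at 94% is about 20–30% for overall accuracy and 9% for specificity. The statement in section 7.2 and the Synopsis that the tests will answer the influence of operator, tumor size and embolization material is not supported.

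The size rests on assumptions: 98% accuracy, one result per patient, a joint model, and the site and TACE-type splits shown. Higher error rates or pooled reads ease the fitting problem considerably. One result does not depend on the 98%: a group that meets its specificity target leaves too few false positives to estimate three sites. This is a defect of specification and of claim in a secondary analysis.

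**What to change.** - Name the outcome, the unit (single reader, majority or all reads), the covariates and the coding of lesion size.
- Drop the ANOVA.
- Model CEUS-positive reads with a patient-clustered logistic model (GEE or mixed) over the reads, with reference status in the model. Otherwise use Firth-penalised logistic models with few covariates, one factor at a time where errors are very sparse, as they will be for specificity. Penalisation gives finite estimates but adds no information.
- Report sensitivity and specificity with exact intervals by site, TACE type and size group, using one result per patient.
- In the Synopsis and section 7.2, say that these analyses will describe the influences rather than answer them, and state that p > 0.05 is not evidence of no dependence.

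The cost is SAP wording and analysis code, with no added patients or imaging. The downside is a weaker claim about site, size and embolization effects.
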